12.4.1.3.4 Sensitivity Analysis

A sensitivity analysis will be performed using a hypothetical strategy. In this approach, the unobserved data following discontinuation for lack of efficacy or AEs will be assumed to follow the placebo distribution at the matching visit, conditioned on the patient's observed data (including Baseline). Patients who discontinue for all other reasons and intermittent missing data will be assumed to be missing at random.

The change from Baseline will be analyzed in an MMRM model run on each of the management of the replicates obtained as per the process described in section 12.4.1.2 and combined using Mianalyze (Rubin 1976). Fixed effects will be included for treatment, Baseline value, visit and a term for the interaction between treatment and visit. An unstructured covariance structure will be utilized; in the case of convergence issues, the same approaches as defined in section 12.4.1.4.3 will be followed; Kenward-Rogers degrees of freedom will be used. LS means, standard errors, and the LS mean differences (each treatment versus placebo and the pooled active groups versus placebo) will be reported. All estimates will be generated from a single model, i.e., the pooled estimates will be created via model contrasts.

12.4.1.4 Key Secondary Efficacy Analyses

Descriptive summary of each of the secondary endpoints will be provided (mean, SD, median, minimum, maximum) for the absolute values and change from Baseline. All summaries will be presented by treatment group and for the active groups combined.

12.4.1.4.1 Caregiver Global Impression of Severity (CaGI-S)

CaGI-S for EDS is a Likert rating scale completed by the parent/caregiver to assess the likelihood of the patient falling asleep during daytime activities with the following possible responses:

Early Termination visits will be summarized under Visit 3, Visit 4, or Visit 5 (depending on the visit they are closest to, per section 9.2) regardless of the discontinuation reason.

Frequency count and percentage of patients for each category and by visit will be provided as well as shift from Baseline. In addition, the number and percentage of patients with at least one-point improvement from Baseline (responder) will be summarized by treatment group and active groups combined. Percentages will be based on the number of patients with non-missing CaGI-S at Baseline and at each post-baseline visit.

The change from Baseline will be analyzed using a MMRM approach. Fixed effects will be included for treatment, visit, treatment*visit interaction and, Baseline value. An unstructured covariance structure will be utilized; in the case of convergence issues, the same approaches as defined in section 12.4.1.4.3 will be followed; Kenward-Rogers degrees of freedom will be used. LS means, SE, and the LS mean differences (each treatment versus placebo and the pooled active groups versus placebo) at each visit will be reported. All estimates will be generated from a single model, i.e., the pooled estimates will be created via model contrasts.

12.4.1.4.2 Clinical Global Impression of Severity (CGI-S)

From protocol version 1 to protocol version 3, CGI-S for overall impression of severity was a Likert-type rating scale completed by the investigator to assess the patient's condition, with the following possible responses:

From protocol version 4, CGI-S for overall impression of severity is a tikert-type rating scale completed by the investigator to assess the patient's condition, with the following possible responses:

For the reporting results from the Likert-type rating scale will be mapped to the Likert-type rating scale as shown in Table 9.

Table 9: Mapping from Likert-type Rating Scale to Likert-type Rating Scale

Likert-type Rating	Likert-type Rating

The same summaries and analysis as performed for CaGI-S will be repeated for the CGI-S endpoint. Further details on the inferential analysis are provided in section 12.4.1.5.1.

In addition, the number and percentage of patients with at least one-point improvement from Baseline (responder) will be summarized by treatment group and active groups combined. Percentages will be based on the number of patients with non-missing CGI-S at Baseline and at each post-baseline visit.

12.4.1.5 Other Secondary Efficacy Analyses

Descriptive summary of each of the other secondary endpoints will be provided (mean, SD, median, minimum, maximum) for the absolute values and change from Baseline. All summaries will be presented by treatment group and for the active groups combined.

[figure not shown]
The other secondary efficacy endpoints are change from Baseline to Week 11 (Visit 5) in the following:

- Behavior as measured by the ABC-2
- Behavioral and cognitive rigidity as measured by the MERS-PWS
- · Psychomotor function as measured by the Cogstate Detection test
- Attention as measured by the Cogstate Identification test
- Working memory as measured by the Cogstate One Back test
- Measure of caregiver burden using the ZBI-22

12.4.1.5.1 Aberrant Behavior Checklist, Second Edition (ABC-2)

The ABC-2 assesses problematic behavior at home, in educational and work settings, and in residential and community-based facilities. The checklist rates 58 specific symptoms and provides comprehensive descriptions for each assessed behavior, divided into five subscales (there is no total score):

- Irritability (15 items)
- Social withdrawal (16 items)
- Stereotypic behavior (7 items)
- Hyperactive/non-compliance (16 items)
- Inappropriate speech (4 items)

The scores from each item are summed in each subscale as shown in Table 10. For a score to be calculated, the number of missing items should be 3 or less for the irritability scale, social withdrawal scale and hyperactivity/non-compliance scale, 2 or less for the stereotypic behavior scale, and 1 or less for the inappropriate speech scale.

The score for each scale will be derived by 1) adding the score for the non-missing items, 2) dividing the sum obtained by the number of items answered and 3) multiplying by the number of items in the scale.

Table 10: ABC-2 Sub-Scales Scoring

Sub-scale	Items #		

The irritability score ranges from the social withdrawal score ranges from the stereotypic behavior score range

The same analysis as performed for CaGI-S will be repeated for the each of the ABC-2 subscales. Further details on the inferential analysis are provided in section 12.4.1.5.1.

[figure not shown]
12.4.1.5.2 Montefiore-Einstein Rigidity Scale-Prader-Willi Syndrome (MERS-PWS)

The MERS-PWS is a clinician-rated, semi-structured interview conducted with both the patient with PWS and caregiver present. The MERS-PWS measures the following three domains of rigid behavior:

- Behavioral Rigidity Domain: difficulty managing behavior in new, unfamiliar, or unexpected situations (e.g., insistence on sameness, things must be done in his/her way, difficulty when a change interrupts plans/activity, etc.)
- Cognitive Rigidity Domain: lack of flexible thinking (e.g., repetitive/perseverative questioning in response to lack of flexible thinking, need to know or check for reassurance, difficulty shifting "gears" and/or conversation topics)
- **Protest Domain:** the behavioral response (i.e., protest) that results from a real or perceived interruption to rigidity (i.e., severity of protest [irritability, verbal objections, tantrums, nonresponsive, etc.], length of protest, interference due to protest, and the effort needed to calm the patient down from the protest)

Within each domain, items are rated on a scale of the scores for each domain are added, and composite scores are calculated (the domains and composite scores are calculated as shown in Table 11. If one or multiple items are missing (not answered), the corresponding domain score and composite score(s) will not be calculated.

[figure not shown]
Table 11: Scoring Rules for MERS-PWS

The behavior rigidity score ranges from the protest score ranges from the protest score ranges from the total domains composite score ranges from the total doma

The same analysis as performed for CaGI-S will be repeated for the each of the MERS-PWS domains and composites scores. Further details on the inferential analysis are provided in section 12.4.1.5.1.

12.4.1.5.3 Cogstate Detection Test

Early Termination visits will be mapped to the closest planned visit (section 9.2) regardless of the discontinuation reason.

The change from Baseline will be analyzed with an MMRM approach. Fixed effects will be included for treatment, visit, treatment*visit interaction and Baseline value. An unstructured covariance structure will be utilized; Kenward-Rogers degrees of freedom will be used.LS means, SE, and the LS mean differences (each treatment versus placebo and the pooled active groups versus placebo) will be reported. All estimates will be generated from a single model, i.e., the pooled estimates will be created via model contrasts. Significance tests will be based on LS means using a single model. The effect size (magnitude of the differences between treatment groups and placebo) will also be provided.

The analysis of the Detection test will be performed by Cogstate: more details are provided in the Cogstate SAP.

12.4.1.5.4 Cogstate Identification Test

The Cogstate Identification test is a computerized measure of visual attention and uses a validated choice RT paradigm with playing card-like stimuli displayed on a computer screen. In this test,

The main

outcome measure for the test is speed of performance (mean of the log₁₀-transformed RTs for correct responses). Decreasing scores represent improved test performance.

Early Termination visits will be mapped to the closest planned visit (section 9.2) regardless of the discontinuation reason.

The same analyses as performed for Cogstate Detection test will be repeated for the Cogstate Identification test endpoint. Further details on the inferential analyses are provided in section 12.4.1.6.3.

12.4.1.5.5 Cogstate One Back Test

The Cogstate One Back Test is a computerized measure of working memory and uses a validated n-back paradigm with playing card stimuli displayed on a screen.

Decreasing

scores represent improved test performance.

Early termination visits will be mapped to the closest planned visit (section 9.2) regardless of the discontinuation reason.

The same analyses as performed for Cogstate Detection test will be repeated for the Cogstate One Back test endpoint. Further details on the inferential analyses are provided in section 12.4.1.6.3.

12.4.1.5.6 22-Items Zarit Burden Interview (ZBI-22)

The ZBI-22 is a self-reported questionnaire in which caregivers are asked to rate their experience on a Likert scale (

) for 22 questions related to caregiver health and psychological well-being, finances, impact on social life, and relationship with the individual with the disability. Responses are summed to derive the ZBI-22 total score (

), where higher scores represent greater burden.

If more than items out of are missing, the score will be set to missing. Otherwise, the score will be derived by 1) adding the non-missing items, 2) dividing the sum obtained by the number of items answered and 3) multiplying by 22.

The same analysis as performed for CaGI-S will be repeated for the ZBI-22 total score. Further details on the inferential analysis are provided in section 12.4.1.5.1.

12.4.1.6 Exploratory Efficacy Analyses

Other exploratory efficacy endpoints include change from Baseline to Week 11 (Visit 5) in each of the following:

- Total score of the Hyperphagia Questionnaire for Clinical Trials (HQ-CT) in conjunction with the Food Safe Zone Questionnaire (FSZQ)
- Acylated and unacylated ghrelin levels
- Exposure-response relationship between plasma pitolisant concentrations and changes in efficacy measures
- Psychomotor/Attention Composite Score
- Psychomotor/Attention/Working Memory Composite Score

12.4.1.6.1 Hyperphagia Questionnaire for Clinical Trials (HQ-CT)

The HQ-CT is a questionnaire designed to measure food-related preoccupations and problems in PWS, as well as the severity of these concerns. The questionnaire is an observer-reported outcome measure, completed by caregivers who report on the patient's hyperphagic symptoms. Higher scores are related to increased hyperphagia. The HQ-CT is used in conjunction with the FSZQ, which assesses the level of food environmental control required for patients.

The HQ-CT total score is derived by summing the item-level responses, yielding a score ranging from ; the computation of an HQ-CT total score requires responses to at least six items, and any missing responses (up to item responses) are replaced with the average of the remaining (completed) item responses.

The same analysis as performed for CaGI-S will be repeated for the HQ-CT total score. Further details on the inferential analysis are provided in section 12.4.1.5.1.

12.4.1.6.2 Food Safe Zone Questionnaire (FSZQ)

The FSZQ is a observer-reported measure of environmental controls that are in place to manage hyperphagia in patients with PWS. The FSZQ is performed in conjunction with the HQCT.

Caregivers will complete this assessment. Higher scores are associated with higher levels of environmental food control, and as patients with PWS respond favorably to treatment, scores are expected to decrease as the level of control over their food environment lessens. If one or more item-scores are missing, the score will be missing.

The same analysis as performed for CaGI-S will be repeated for the FSZQ total score. Further details on the inferential analysis are provided in section 12.4.1.5.1.

12.4.1.6.3 Serum Ghrelin Levels

Samples for serum ghrelin levels (acylated and unacylated) will be collected while the patient is fasting and may be collected at the same time as sample collection for clinical laboratory tests.

The change from Baseline will be analyzed in an ANCOVA model. Fixed effects will be included for treatment and Baseline value. LS means, SE, and the LS mean differences (each treatment versus placebo and the pooled active groups versus placebo) will be reported. All estimates will

be generated from a single model, i.e., the pooled estimates will be created via model contrasts. Significance tests will be based on LS means using a

12.4.1.6.4 Multiple Sleep Latency Test (MSLT)

The multiple sleep latency test (MSLT) is not collected starting with the protocol version 6, therefore only a summary table and listing will be provided.

MSLT is a standard tool that tests for EDS by measuring how quickly a patient falls asleep in a quiet environment during the day. The MSLT is a full-day test

The mean of the sleep latency will be derived using the sleep latency obtained from only valid assessments will be considered. The assessment from a nap will be deemed valid if the duration of the sleep time for that nap is will be excluded from the average as it is assumed the results from the last naps will be overinflated. If there is only one valid nap, the average will not be derived and therefore will not be included in the summary table.

The mean of the sleep latency and its change from Baseline will be summarized (for the data collected) and listed.

12.4.1.6.5 Subgroup Analysis

Subgroups analysis for each age group (6 to <12 years; 12 to <18 years and 18 years or older) will be conducted for the following endpoints:

- Change in mean score from Baseline in ESS-CHAD (parent/caregiver version) at Visit 3,
 Visit 4 and Visit 5
- Change from Baseline in CaGI-S at Visit 3, Visit 4 and Visit 5
- Change from Baseline in CGI-S at Visit 3, Visit 4 and Visit 5
- Change from baseline in HQ-CT at Visit 3, Visit 4 and Visit 5
- Change from Baseline in acylated ghrelin levels at Visit 5
- Change from Baseline in unacylated ghrelin levels at Visit 5

Subgroups analysis for patients with/without concomitant sleep disorders that could potentially contribute to EDS beyond the EDS associated with PWS, and sleep disorder symptoms will be conducted for the following endpoints. Medical terms that are specifically used to describe EDS (e.g., hypersomnia, hypersomnolence, sleepiness, etc.) will not be used to infer a concomitant sleep disorder or sleep disorder symptom as EDS is required for study entry.

A manual review of the medical history for each patient will be performed by a blinded medically trained person(s) to determine which patients have sleep disorders, or comorbidity(es) associated with sleep disorder(s) that may contribute to EDS, apart from medical terms that are specifically used to describe EDS (e.g., hypersomnia, hypersomnolence, sleepiness, etc.). The final

determination and approval by Harmony Biosciences will be conducted on clean data and prior to unblinding of the Double-Blind Treatment Phase.

- Change in mean score from Baseline in ESS-CHAD (parent/caregiver version) at Visit 3,
 Visit 4 and Visit 5
- Change from Baseline in CaGI-S at Visit 3, Visit 4 and Visit 5
- Change from Baseline in CGI-S at Visit 3, Visit 4 and Visit 5

Summary for actuals and change from Baseline by treatment groups (low dose, high dose, pooled active doses and placebo) will be provided for each endpoint and subgroup.

Inferential statistics will be derived if the sample size in each subgroup is strictly greater than The MMRM approach with fixed effects of Baseline value, visit and a term for the interaction between treatment and visit will be implemented. An unstructured covariance structure will be utilized; Kenward-Rogers degrees of freedom will be used.

In the case of convergence issues, the following steps will be implemented (in the order listed) until convergence is reached.

- 1. The Fisher scoring algorithm will be used to start the first iteration to obtain the initial values of the covariate parameters (via the SCORING option of the PROC MIXED statement).
- 2. The no-diagonal factor analytic structure (via the TYPE=FA0(T) option of the REPEATED statement, where T is the total number of time points).
- 3. Covariance matrix of ARH(1) (Heterogeneous auto-regressive 1), and CS (compound symmetry) with the sandwich variance estimator will be used in that order (for the sandwich variance estimator Kenward-Rogers degrees of freedom will be replaced by the EMPIRICAL option).

The MMRM will be replaced with an ANCOVA (with treatment and Baseline as fixed effect) or a simple t-test if sample size does not permit more complicated modeling approaches within a subgroup (i.e., in case of convergence issues, or the difference in the change from Baseline cannot be estimated).

12.4.1.6.6 Exposure-response relationship between plasma pitolisant concentrations and changes in efficacy measures

The following plots will be produced to evaluate to exposure-response between the plasma pitolisant concentrations and change in efficacy measures. Only the plots with sufficient data will be produced (e.g.,

- Panel plot of mean plasma pitolisant concentration over time (linear and semi-logarithmic scales) by ESS-CHAD (parent/caregiver version) responder status at Visit 5 (responder and non-responder), treatment group (low dose, high dose and pooled active doses) and/or age groups. Patients with no post-baseline ESS-CHAD (parent/caregiver version) will not be included in the plots.
- Panel plot of mean plasma pitolisant concentration over time (linear and semi-logarithmic scales) by CaGI-S categories (no improvement or worsening vs. improvement at Visit 5),

treatment group (low dose, high dose and pooled active doses) and/or age groups. Patients with no CaGI-S assessment at Visit 5 will not be included in the plots.

- Panel plot of mean plasma pitolisant concentration over time (linear and semi-logarithmic scales) by CGI-S categories (no improvement or worsening vs. improvement at Visit 5), treatment group (low dose, high dose and pooled active doses) and/or age groups. Patients with no CGI-S assessment at Visit 5 will not be included in the plots.
- Further plots and analysis of relationship between plasma pitolisant concentrations and change in efficacy measures may be investigated.

12.4.1.6.7 Cogstate Psychomotor/Attention Composite Score and Psychomotor/Attention/ Working Memory Composite Score

The Cogstate Psychomotor/Attention Composite Score will be derived from Cogstate Detection test and Cogstate Identification test by standardizing the test scores against the performance score of the study sample at Baseline. If z-scores are available (i.e., non-missing) for both tests, then they will be averaged to compute the Psychomotor/Attention Composite Score.

Similarly, the Cogstate Psychomotor/Attention/Working Memory Composite Score will be derived from Cogstate Detection test, Cogstate Identification test and One Back test by standardizing the test scores against the performance score of the study sample at Baseline. If z-scores are available (i.e., non-missing) for all three tests, then they will be averaged to compute the Psychomotor/Attention/Working Memory Composite Score.

The same analyses as performed for cogstate Detection test will be repeated for the each of the composite score. Further details on the inferential analyses are provided in section 12.4.1.6.3.

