2.3. Exploratory Objectives

The exploratory objectives of this study are to evaluate the following in patients with PWS ages 6 to 65 years:

- The impact of pitolisant on hyperphagia
- The impact of pitolisant on ghrelin levels
- The PK of pitolisant and its major metabolite, BP1.3484
- The relationship between levels of pitolisant (PK) and treatment effect (pharmacodynamics)

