3.2.2. Pharmacokinetic and Pharmacodynamic Endpoints

• C_{max} of pitolisant and its major metabolite, BP1.3484

- Area under the concentration-time curve from time 0 to the last collection time (AUC_{last}) after administration of pitolisant
- Time to observed maximum concentration (t_{max}) of pitolisant
- Exposure-response relationship between pitolisant levels and change in efficacy measures

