D11	Visit 3	Visit 3 (Day 22)	22	2	35
Double- Blind	Visit 4	Visit 4 (Day 50)	50	36	63

Abbreviations: ABC-2 = Aberrant Behavior Checklist, Second Edition; ADAMS = Anxiety, Depression, and Mood Scale; C-SSRS = Columbia-Suicide Severity Rating Scale; CAGI-S = Caregiver Global Impression of Severity; CGI-S = Clinical Global Impression of Severity; ECG = electrocardiogram; ESS-CHAD = Epworth Sleepiness Scale for Children and Adolescents; FSZQ = Food Safe Zone Questionnaire; HQ-CT = Hyperphagia Questionnaire for Clinical Trials; MERS-PWS = Montefiore-Einstein Rigidity Scale – Prader-Willi Syndrome; PWS = Prader-Willi Syndrome; ZBI-22 = 22-item Zarit Burden Interview.

Note: For MSLT, C-SSRS and ADAMS no analysis window will be applied; data will be reported using the nominal visit.

Table 6: PK Draw Timing

Visit	Target Day		
Visit 3	Day 22	Any time after the morning dose of the study drug	
Visit 4	Day 50	 Pre-dose Between 45 and 75 minutes after dosing, Between 1.5 and 2.5 hours after dosing, Between 3.0 and 4.0 hours after dosing, Between 5.0 and 6.0 hours after dosing 	
Visit 5	77	Any time after the morning dose of the study drug	

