10.4 Pharmacokinetic Population

The PK population will include all patients who received at least one dose of study drug and have a non-missing pitolisant PK concentration. Patients will be analyzed by treatment (high dose and low dose), active arms pooled, and overall (placebo patients will be excluded from the PK population).

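### The exposure-response endpoint rests on mean-concentration plots by responder category; no patient's own exposure is set against that patient's own change

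*SAP*

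**What the plan says.** Protocol 3.2.2 lists among its PK and pharmacodynamic endpoints the "Exposure-response relationship between pitolisant levels and change in efficacy measures". Protocol 2.3 and SAP 7.3 place the matching objective among the exploratory ones.

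SAP 12.4.1.6.6 gives the method: "The following plots will be produced to evaluate to exposure-response between the plasma pitolisant concentrations and change in efficacy measures". Three figures follow. The first is a "Panel plot of mean plasma pitolisant concentration over time (linear and semi-logarithmic scales) by ESS-CHAD (parent/caregiver version) responder status at Visit 5". The second has the same layout, drawn "by CaGI-S categories (no improvement or worsening vs. improvement at Visit 5", and the third does the same for CGI-S. All three are arranged by "treatment group (low dose, high dose and pooled active doses) and/or age groups". Only plots with enough data are to be produced; the threshold is blacked out.

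The section ends by leaving other plots and analyses open, without naming an exposure metric, an outcome or a model. SAP 12.5 makes population PK optional, post hoc and separately reported. It also derives Cmax and AUC for each patient where the data allow, but does not link them to efficacy. Under SAP 10.4, "placebo patients will be excluded from the PK population".

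**The concern.** The endpoint asks how change depends on exposure. The committed plots turn this round: concentration is the plotted quantity and the outcome becomes a grouping variable with two levels. No effect per unit of exposure can be read from such a figure, and no interval shows how uncertain it is. Three things are lost:

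- The size of each patient's change, because the outcome is reduced to responder or not, or improved or not.
- Each patient's own exposure, because concentrations are averaged within groups.
- The pairing of the two, although both are available for the same patient.

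Among the endpoints listed at the start of SAP 12.4.1.6, this is the only one without a committed model or estimate. HQ-CT and the Cogstate composites have an MMRM, and ghrelin has an ANCOVA.

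The trial is meant to inform later studies (Protocol 9.1.2), and Protocol 1.2 says that PK characterisation will inform dose selection. At stake is the quality of the exposure information carried forward, including the risk that two similar-looking mean curves are taken as evidence of no relationship.

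**Working it through.** The documents state no figure for this endpoint. The check reproduces the design figures that supply its inputs, then compares analyses.

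**1. Design figures (Protocol 9.2).** Inputs: 20 patients per arm, SD 5 to 6, and a difference of 3.9 between pooled pitolisant (n = 40) and placebo (n = 20).

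- SE at SD 5 = 5 × √(1/40 + 1/20) = 1.369, and 3.9 / 1.369 = 2.85.
- Two-sided 5% power is 80.0% by non-central t (58 df) and 81.3% by the normal approximation. Stated: 80%.
- 95% half-width = 1.96 × 1.369 = 2.68 at SD 5, and 1.96 × 6 × √(1/40 + 1/20) = 3.22 at SD 6. Stated: 2.7 and 3.2.

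All of these reproduce, so no stated figure is wrong.

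**2. Cost of splitting the outcome.** For a normal outcome cut so that a share p responds, the information kept is φ(z_p)² / [p(1 − p)]. This is 0.637 at p = 0.5 and 0.576 at p = 0.3. The 40 active patients then act like 40 × 0.576 = 23.0 to 40 × 0.637 = 25.5.

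**3. Simulation in active patients.** There were 4,000 trials per setting, with 20 low-dose and 20 high-dose patients. Assumptions not in the documents:

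- exposure proportional to dose (high = 2 × low), with between-patient CV 40-80%
- effect linear in exposure
- responders split at the median (the SAP cut-off is blacked out)
- two-sided 0.05 (the SAP level is blacked out; 0.05 matches the 95% intervals)

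With 3.9 points at the mean high-dose exposure, the share of trials detecting the relationship is:

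| Exposure CV | SD | Responder vs non-responder exposure | Individual change on individual exposure |
|---|---|---|---|
| 40% | 5 | 30% | 47% |
| 40% | 6 | 23% | 36% |
| 60% | 5 | 41% | 68% |
| 60% | 6 | 31% | 54% |
| 80% | 5 | 49% | 80% |
| 80% | 6 | 38% | 68% |

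A variant with CV 40-70%, 30% or 50% responders and log exposure in the group comparison gave 22-49% against 35-75%.

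**4. Where the 3.9 applies.** Protocol 9.2 attaches 3.9 to the pooled doses. Putting it at the high dose implies 1.95 at the low dose and a pooled effect of (3.9 + 1.95) / 2 = 2.9. Taking 3.9 as the pooled effect implies 3.9 / 0.75 = 5.2 at the high dose. The ranges then become about 36-69% for the responder split and 55-93% for individual regression. The levels rise and the ordering does not change.

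**5. Would adding placebo at zero exposure help?** Simulate an on/off effect: 3.9 points in every treated patient, unrelated to exposure. One slope through all 60 patients, with placebo at zero, is significant in about 24-52% of trials. The active-only regression stays at about 4-5%.

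**The case against.** The strongest reply is that this is an exploratory objective in a proof-of-concept study that SAP 12.4.1.1 says is not powered for significance. Describing first and modelling later is a legitimate choice with 40 active patients. Individual concentrations and PK parameters will exist, so nothing is lost for good, and the SAP leaves room for further work. The plots carry no test, so a power comparison is only a proxy for what a reader could see in them. Exposure variability, linearity and the responder share are all assumed. CaGI-S and CGI-S are single items with five and four levels (Protocol 6.3.2 and 6.3.3), so splitting them discards less than splitting ESS-CHAD does.

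All of this limits the weight of the point. It does not supply a committed analysis of the relationship that the endpoint names.

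A reader might also infer four stronger things, which the documents do not support:

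- **That leaving out placebo is a defect.** Placebo patients have no pitolisant level to plot, so SAP 10.4 follows from the display. Under the first set of assumptions, a regression with placebo at zero reaches 66-92%. That figure mixes in the drug-versus-placebo contrast, which the MMRM already estimates, and step 5 shows how it misleads.
- **That the plots could show almost nothing.** If 3.9 is the pooled effect, the underlying comparison reaches 36-69%.
- **That each curve averages about three patients.** 40 / 12 is a worst case. The age split is optional, a pooled panel is listed, and a sufficient-data rule applies.
- **That loosely timed Visit 3 and Visit 5 samples blur the curves.** SAP Table 6 allows them "Any time after the morning dose of the study drug", but nothing says that they enter these plots. SAP 12.5 plots means at the midpoints of planned intervals, and only Visit 4 has defined post-dose intervals.

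**Conclusion.** The point holds as a moderate weakness in the choice of analysis. The committed plots dichotomise change, average exposure and never join the two within a patient. In every setting of the table in step 3, relating individual change to individual exposure among the same active patients detects the assumed relationship more often: about 36-80% against 23-49% with 3.9 points at the high dose. With 3.9 as the pooled effect, the ranges are 55-93% against 36-69%. The size of the gap depends on the assumed CV, linearity and responder split, and it was worked out for ESS-CHAD only. The consequence is weaker exposure information for later studies; the primary and secondary analyses are unaffected.

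**What to change.** In SAP 12.4.1.6.6, specify a scatter plot of individual change from Baseline at Visit 5 against individual Visit 4 AUClast and Cmax in pitolisant-treated patients. Take ESS-CHAD first, then CaGI-S and CGI-S. Mark points by dose and age band, and report a baseline-adjusted slope with its 95% CI. Show placebo patients for reference or in a secondary model only, not in the main slope. Keep the responder and improvement panels as supplementary.

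Protocol 1.3.2 describes the Double-Blind Treatment Phase as completed. If the analysis is added after unblinding, label it post hoc.

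The cost is SAP wording plus one exploratory figure and table from data already collected, with no new samples. The downside is a wide interval with at most 40 patients, fewer where PK parameters cannot be derived.
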